8.2 Statistical Analyses

8.2.1 Descriptive endpoints

The endpoints for evaluating the main study objectives are described in section 4.1.

8.2.2 Analysis Methodology

The endpoints will be summarized descriptively based on available data or measurements in the analysis population. No formal hypothesis testing will be performed.

In general, continuous variables will be summarized with the numbers of observations, means with standard deviations, quartiles, minimums, maximums, and 95% confidence intervals for the means as per the table mockups.

Categorical variables will be summarized with subject counts and percentages/rates, and where specified in the table mockups, with exact 95% Clopper-Pearson confidence intervals.

All pre-defined adverse events will be captured. Only adverse events that occur after HD Grid catheter is inserted (after enrollment) will be analyzed, as defined in the safety analysis population. Tables will be created that show incidences of all ADEs. Cardiovascular serious adverse events will be analyzed and reported in a similar manner as ADEs.

Survival analysis will be conducted to analyze time-to-event variables. Events occurring during the 90 days following the ablation procedure for PersAF subjects (90-day blanking period) or 14-day blanking period following the ablation procedure for VT subjects will not be counted as an effectiveness outcome failure. Subjects without events will be censored at their last known event-free time point. Subjects withdrawn or otherwise lost-to-follow-up during the follow-up period will be censored at their last known visit. Survival data will be presented using the Kaplan-Meier product limit method.

8.4 Timing of Analysis

Data analyses will be performed at the completion of the 12-month follow-up period for all subjects or as desired by Sponsor.

In addition, study progress and data may be summarized and reported as needed.

8.5 Subgroup Analysis

There are no pre-specified subgroup analyses planned for this clinical study. Although, all descriptive endpoints will be analyzed separately for PersAF and VT populations.

Clinical Investigation Plan

8.6 Multiplicity

No hypothesis testing will be performed; therefore, no adjustments will be made for multiplicity in the endpoint analyses.

8.7 Procedures for Accounting for Missing Data

Every effort will be made to collect all required data. All data available for the endpoints specified among the analysis population will be used. Missing data will not be imputed. Kaplan-Meier analysis will censor subjects withdrawn or otherwise lost-to-follow-up at last known visit.

8.8 Planned Interim Analysis

An interim analysis of acute descriptive endpoints related to the use of HD Grid and the Precision system with HD Wave will be performed when 250 subjects have been enrolled and completed the procedure visit and related data collection.

8.9 Statistical Criteria for Termination

There are no statistical criteria for termination of this clinical study.

8.10 Success Criteria

Pass/Fail criteria do not apply to this study.

8.11 Deviations from Statistical Plan

Any major changes or less significant changes to the planned statistical analyses will be documented in the final report.

8.12 Analysis of Baseline Data

Tables will be created to define the study population at baseline. Tables will include demographics, physical examination, cardiac history, arrhythmia history, 12-lead ECG, antiarrhythmic/anticoagulant medication use, and QOL data.

8.13 Analysis of Quality of Life

The EQ-5D/AFEQT questionnaires will be analyzed for subjects treated for Persistent AF, and the EQ-5D/HADS questionnaires will be analyzed for subjects treated for VT. Data will be assessed at baseline and then at 6 and 12 months. Data will be compared at each assessment interval to the baseline score.

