4.1.3 Additional descriptive endpoints

Additional descriptive endpoints include:

- Change in quality of life (QOL) at 6 and 12 months after receiving HD Grid mapping and RF ablation relative to baseline: defined as change in quality of life assessed in validated QOL surveys (EQ-5D and AFEQT for subjects with PersAF, EQ-5D and HADS for subjects with VT)
- Rate of periprocedural and immediate post procedural (48hrs) procedure- or device- related adverse events in all subjects in whom the HD Grid is inserted (regardless of RF energy delivery).
- Rate of procedure- or device-related adverse events and cardiovascular serious adverse events in all subjects in whom the HD Grid is inserted (regardless of RF energy delivery) through 30 days post study procedure.
- Proportion of VT subjects who receive HD Grid mapping and RF energy delivery free from recurrence of sustained monomorphic VT and new or increased dose of class I/III AAD, and free from recurrence of sustained monomorphic VT on or off class I/III AADs at 12-month follow-up outside the blanking period.
- Rate of repeat ablations after study procedure during 12-month follow up defined as proportion of subjects without an additional ablation procedure to treat indicated cardiac arrhythmia (outside blanking period, if applicable).
- For subjects treated for PersAF:
 - Proportion with atypical atrial flutter (AFL) identified during procedure
 - Of those receiving HD Grid mapping and RF ablation for AFL: Utility of HD Grid specific to the identification and treatment of atypical AFL (as defined in section 4.1.2), including role of HD wave relative to along-the-spline maps in identifying ablation target(s), and time of RF application to terminate atypical AFL

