5.5.1 Lost-to-Follow-up

If the subject misses any scheduled follow-up visit, attempts at contacting the subject as detailed below will be made within the follow-up visit window. If a subject misses the 6-month follow-up visit it will be considered a missed visit. If the attempts at contacting the subject detailed below are unsuccessful for the 12-month visit, then the subject is considered lost-to-follow-up. Site personnel shall make all reasonable efforts to locate and communicate with the subject (and document these efforts in the source documents), including the following, at each contact time point:

- A minimum of two telephone calls on different days over the specified follow-up windows to contact the subject should be recorded in the source documentation, including date, time and initials of site personnel trying to make contact.
- If these attempts are unsuccessful, a letter (certified if applicable) should be sent to the subject.

[REDACTED]

[REDACTED]

[REDACTED]

[REDACTED]

[REDACTED]

[REDACTED]

[REDACTED]

Clinical Investigation Plan

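### Quality-of-life change is summarised on available scores only, so drop-out related to scores already observed could bias it in either direction; a supportive repeated-measures analysis would address that part.

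*Combined protocol and SAP*

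**What the plan says.** Section 4.1.3 lists as an additional descriptive endpoint: "Change in quality of life (QOL) at 6 and 12 months after receiving HD Grid mapping and RF ablation relative to baseline". The questionnaires are EQ-5D and AFEQT for persistent AF, and EQ-5D and HADS for VT.

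Section 8.13 gives the method in two sentences: "Data will be assessed at baseline and then at 6 and 12 months", and "Data will be compared at each assessment interval to the baseline score". It names no model and does not say whether the comparison is paired.

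Two general rules fill in the rest. Section 8.2.2: "The endpoints will be summarized descriptively based on available data or measurements in the analysis population". Section 8.7: "Missing data will not be imputed". Continuous variables are reported with the number of observations and "means with standard deviations, quartiles, minimums, maximums, and 95% confidence intervals for the means as per the table mockups". The one specific rule for drop-outs is Kaplan-Meier censoring, which does not apply to questionnaire scores.

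Missing scores are foreseen. Section 5.5.1 says: "If a subject misses the 6-month follow-up visit it will be considered a missed visit". Section 5.5 lists death and withdrawal as reasons for discontinuation, and after withdrawal only vital status is recorded, for up to 30 days.

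**The concern.** Read together, these sections describe a visit-by-visit summary of whoever has a score. The 12-month result leaves out every subject without a 12-month score, and any 6-month score that subject gave goes unused. The 6-month and 12-month changes may also rest on somewhat different, though largely overlapping, sets of subjects.

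A mean paired change is unbiased if non-response is unrelated to the change itself. If response depends on an observed score that is correlated with the change, the respondents' mean change is not the cohort's mean change. A single-arm study has no second group in which similar drop-out might offset the error. The reported confidence interval for the mean does not reflect the problem.

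**Working it through.** The readable text gives no SD, correlation, drop-out rate or expected change for quality of life, so there is no planned figure to reproduce. Every input below is an assumption chosen to show scale.

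**Inputs**
- SD of 20 points at each visit; a higher score is better (signs reverse on a scale where higher is worse).
- Correlations: baseline with 6 months 0.5, baseline with 12 months 0.5, 6 with 12 months 0.7.
- 15% or 25% missing at 12 months, with all baseline and 6-month scores present.
- Odds of missing 12 months 1.65 times higher per 10 points worse on the driving score. Since ln 1.65 = 0.5, this is a log-odds of 1 per SD.
- 350 subjects in the indication, used only for the confidence interval. The documents give 500 in total and no readable split.

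**Step 1: selection on the driving score.** Let z be the driving score in SD units and P(missing | z) = 1/(1 + exp(z - a)), with a solved to give the stated proportion missing. Let d be the mean of z among respondents. Numerical integration over a standard normal z gives d = 0.133 at 15% missing (a = -2.05) and d = 0.213 at 25% (a = -1.31).

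**Step 2: bias of the paired available-case change at 12 months.** For jointly normal scores,

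bias = 20 × [corr(12-month score, z) - corr(baseline score, z)] × d.

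When z is the 6-month change, its SD is 20 × √(2 - 2 × 0.5) = 20, and the bracket is 0.7 - 0.5 - 0.5 + 1 = 0.7.

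| Score driving drop-out | Bracket | Bias, 15% missing | Bias, 25% missing |
|---|---|---|---|
| Baseline | 0.5 - 1 = -0.5 | -1.3 | -2.1 |
| 6-month level | 0.7 - 0.5 = 0.2 | +0.5 | +0.9 |
| 6-month change | 0.7 | +1.9 | +3.0 |
| Unseen 12-month level | 1 - 0.5 = 0.5 | +1.3 | +2.1 |

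Simulation with 2,000,000 subjects per setting agrees within 0.1 point. With all three correlations at 0.5, the bracket for the 6-month level is 0.5 - 0.5 = 0, so there is no bias even though response depends on the score.

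**Step 3: the repeated-measures estimate.** In the same simulations a likelihood estimate with free means and unstructured covariance has bias of about 0 in the first three rows. In the fourth row it gains nothing: 1.3 against 1.3 at 15% missing, and 2.2 against 2.1 at 25%. With all correlations at 0.5 it does worse there: about 1.8 against 1.3, and 3.0 against 2.1.

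**Step 4: scale.** The SD of the change is 20 × √(2 × (1 - 0.5)) = 20. The 95% half-width is 1.96 × 20/√(350 × 0.85) = 2.3 points at 15% missing and 1.96 × 20/√(350 × 0.75) = 2.4 at 25%. The bias is below the half-width in every row except the 6-month-change row at 25% missing. When the 6-month level drives drop-out, the model's standard error is about 3% smaller at 15% missing and 6% to 7% smaller at 25%.

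**Step 5: paired or unpaired.** With correlations 0.5, 0.4 and 0.7 (baseline with 6 months, baseline with 12 months, 6 with 12 months), 10% to 30% missing, and baseline-driven drop-out, the paired change is understated by 0.05 to 0.15 SD. The mean of 12-month respondents minus the mean of all baselines overstates it by 0.04 to 0.10 SD. The sign depends on a choice that section 8.13 leaves open.

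**The case against.** The strongest reply is that an observed-case summary suits the purpose. Quality of life is an additional descriptive endpoint, section 8.2.2 says "No formal hypothesis testing will be performed", and section 8.10 sets no pass/fail criterion. The plan also limits and documents missing data: contact attempts in 5.5.1, 6-month visits by telephone and windows of ±90 days in 6.4.1, completeness checks on questionnaires in 6.4.4, reasons for discontinuation sent to the sponsor under 5.5, and numbers of observations in every continuous summary. Section 8.2.2 defers to table mock-ups that are not in the text supplied, and part of 8.1 is redacted, so more detail may exist there. All of this stands, and it keeps the point minor. It does not say how the remaining missing scores bear on the result.

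A reader might infer that drop-out inflates the gain and so favours the procedure, because subjects who do badly stay away. The documents do not say who is likely to be missing, and the table above shows a bias of either sign. Nor does any dependence of response on score produce bias, as the equal-correlation case shows.

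**Conclusion.** The gap is real but modest. The 12-month quality-of-life result ignores known earlier scores of subjects without 12-month data. If drop-out relates to those scores, the mean paired change may be off by roughly -2 to +3 points, under the assumed SD of 20, the assumed correlations and strength of dependence, and 15% to 25% missing. Real values could be smaller or larger.

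A repeated-measures model removes this part of the bias whichever way it runs. The stronger reading, that the model would cure drop-out bias in general, is not supported: it assumes missing at random and can do no better, or worse, when the unseen score decides who responds. It belongs beside the planned summary, not in its place.

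**What to change.** In section 8.13:

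- State that the main summary is the paired change among subjects with both scores, for each indication.
- Add, as a supportive analysis within each indication, a mixed model for repeated measures with baseline, 6-month and 12-month scores as responses, unstructured covariance and all available scores. Report the estimated change at each visit with a 95% confidence interval and no test.
- Tabulate the number missing and the reason at each visit, and compare baseline and 6-month scores between subjects with and without 12-month data.
- Report deaths separately. State that the model implicitly extrapolates scores beyond death; it should not be labelled an estimate for subjects alive.
- Add a sensitivity analysis that shifts the missing 12-month scores by a stated amount. If a fraction m is missing and the shift is s points, the mean change moves by m × s; for example, 0.25 × 10 = 2.5 points.

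The model imputes nothing, so it fits section 8.7. One line there should say that the shift is a sensitivity calculation only. The cost is one model per questionnaire score within each indication, at least four, using data already collected. The downside is the reliance on missing at random for a modest gain.

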8.14 Poolability Assessment

An analysis will be conducted to determine if there is a site bias on descriptive endpoint analyses including acute-and long-term outcomes, procedure time, RF time, fluoroscopy time, and mapping time. Sites enrolling small (one through five) and moderate (six through 15) numbers of subjects will be pooled

Clinical Investigation Plan

into small and moderate enrollers and sites enrolling large (more than 15) numbers of subjects will be included in the analysis as individual sites.

9 DIRECT ACCESS TO SOURCE DATA/DOCUMENTS

The investigator/institution will permit direct access to source data/documents for the purpose of performing clinical study-related monitoring, audits, IRB/EC review and regulatory inspections.

Subjects providing informed consent are agreeing to allow clinical study monitors or regulatory authorities to review, in confidence, any records identifying the subjects in this clinical study. This information may be shared with regulatory agencies; however, Sponsor undertakes not to otherwise release the subject's personal and private information.

10 QUALITY CONTROL AND QUALITY ASSURANCE

10.1 Selection of Clinical Sites and Investigators

The Sponsor will select investigators qualified by training and experience to participate in the clinical study. Sites will be selected based upon review of a recent site assessment, if applicable, and the qualifications of the investigators who will participate in the clinical study.

10.2 CIP Amendments

Approved CIP amendments will be provided to the Investigators by the Sponsor prior to implementing the amendment. The Principal Investigator is responsible for notifying the IRB/EC or equivalent committee of the CIP amendment (administrative changes) or obtaining IRB's/EC's approval of the CIP amendment (changes in subject care or safety), according to the instructions provided by the Sponsor with the CIP amendment.

Acknowledgement/approval by the IRB/EC of the CIP amendment must be documented in writing prior to implementation of the CIP amendment. Copies of this documentation must also be provided to the Sponsor.

10.3 Training

10.3.1 Site Training

All Investigators and clinical study personnel are required to attend Sponsor training sessions, which may be conducted at an Investigator's meeting, a site initiation visit or other appropriate training sessions. Over-the-phone or self-training may take place as required. Training of Investigators and clinical study personnel will include, but is not limited to, the CIP requirements, devices used in this study, electronic case report form completion and clinical study personnel responsibilities. All Investigators and clinical study personnel that are trained must sign a training log (or an equivalent) upon completion of the training. Prior to signing the training log, Investigators and clinical study personnel must not perform any CIP-related activities that are not considered standard of care at the site.

Clinical Investigation Plan

10.3.2 Training Required for the Use of the Device

All investigators involved in the conduct of this clinical study will be qualified by education, training, or experience to perform their tasks and this training will be documented appropriately. Each physician participating in the study procedure must have experience using HD Grid and EnSite Precision for PersAF and/or VT treatment prior to participation in the study.

10.4 Monitoring

It is the responsibility of the Sponsor to ensure the clinical study is conducted, recorded and reported according to the approved CIP, subsequent amendment(s), applicable regulations and guidance documents.

Centralized monitoring will occur through routine internal data review. This monitoring is designed to identify missing and inconsistent data, data outliers, and potential CIP deviations that may be indicative of site non-compliance. On-site monitoring may occur at the discretion of the Sponsor.

10.5 Deviations from CIP

The Investigator should not deviate from the CIP for any reason except in cases of medical emergencies when the deviation is necessary to protect the rights, safety and well-being of the subject or eliminate an apparent immediate hazard to the subject. In that event, the Investigator will notify the Sponsor immediately by phone or in writing.

No waivers for CIP deviations will be granted by the Sponsor. All deviations must be reported to the Sponsor using the Deviation CRF. The occurrence of CIP deviations will be monitored by the Sponsor for evaluation of investigator compliance to the CIP and regulatory requirements and dealt with according to written procedures. Investigators will inform their IRB/EC or equivalent committee of all CIP deviations in accordance with their specific IRB/EC or equivalent committee reporting policies and procedures.

In the event of repeated non-compliance, as determined by the Sponsor, a Sponsor's monitor or company representative will attempt to secure compliance by one or more of the following (and not limited to):

- Visiting the investigator and/or delegate
- Telephoning the investigator and/or delegate
- Corresponding with the investigator and/or delegate

Repeated non-compliance with the signed agreement, the CIP or any other conditions of the clinical study may result in further escalation in accordance with the Sponsor's written procedures, including securing compliance or, at its sole discretion, Sponsor may terminate the investigator's participation in the clinical study.

10.6 Quality Assurance Audit

A Sponsor representative or designee may request access to all clinical study records, including source documentation, for inspection during a Quality Assurance audit.

Clinical Investigation Plan

In the event that an investigator is contacted by a Regulatory Agency in relation to this clinical study, the Investigator will notify Sponsor immediately. The Investigator and Research Coordinator must be available to respond to reasonable requests and audit queries made during the audit process. The Investigator must provide Sponsor with copies of all correspondence that may affect the review of the current clinical study (e.g., Form FDA 483, Inspectional Observations, Warning Letters, Inspection Reports, etc.). Sponsor may provide any needed assistance in responding to regulatory audits.

10.7 Committees

10.7.1 Publications Committee

A Publication Committee may be established to oversee clinical study publications, including publication planning and authorship determinations in alignment with the study publication plan. Publication Committee membership may include investigational site Principal Investigators, a representative of the Sponsor, and a statistician. The Publication Committee may determine policy and strategies regarding individual presentations and/or publications arising from clinical study generated data. The committee may also review all external requests for accessing clinical study-related data and strategies aligning with the Sponsor's presentation and publication team expectations. The committee will also follow the Sponsor's applicable policies and Standard Operating Procedures.

11 DATA HANDLING AND RECORD KEEPING

Sponsor and/or its affiliates will maintain documentation of the systems and procedures used in data collection for the duration of the clinical study.

CRF data collection will be performed through a secure web portal and only authorized personnel will access the Electronic Data Capture (EDC) system using a unique username and password to enter, review or correct data. Passwords and electronic signatures will be strictly confidential.

The data will be subjected to consistency and validation checks within the EDC system and supplemental review by the Sponsor.

At the conclusion of the clinical study, completed CRF images with the date-and-time stamped electronic audit trail indicating the user, the data entered, and any reason for change (if applicable) will be provided to the investigational sites, if requested.

For the duration of the clinical study, the Investigator will maintain complete and accurate documentation including, but not limited to, medical records, clinical study progress records, laboratory reports, CRFs, signed ICFs, device accountability records (if applicable), correspondence with the IRB/EC and clinical study monitor/Sponsor, adverse event reports, and information regarding subject discontinuation or completion of the clinical study.

11.1 Protection of Personally Identifiable Information

The Sponsor respects and protects personally identifiable information collected or maintained for this clinical study. The privacy of each subject and confidentiality of his/her information will be preserved in reports and when publishing any data. Confidentiality of data will be observed by all parties involved at all times throughout the clinical study. All data will be secured against unauthorized access.

Clinical Investigation Plan

